## **9.1.8 Treatment Administration**

Interruptions from the protocol-specified treatment plan for greater than 12 weeks between pembrolizumab doses require consultation between the investigator and the Sponsor and written documentation of the collaborative decision on participant management.

Administration of trial medication will be monitored by the investigator and/or institution staff. The total volume of pembrolizumab infused will be compared to the total volume prepared to determine compliance with each dose of pembrolizumab administered.

### **9.1.8.1 Timing of Dose Administration**

Not applicable.

### **9.1.9 Withdrawal/Discontinuation**

Participants who discontinue study treatment prior to completion of the treatment regimen should be encouraged to continue to be followed for all remaining study visits.

When a participant withdraws from participation in the study, all applicable activities scheduled for the final study visit should be performed at the time of withdrawal. Any adverse events which are present at the time of withdrawal should be followed in accordance with the safety requirements outlined in Section 9.3 - Adverse Events, Serious Adverse Events and Other Reportable Safety Events.

#### **9.1.9.1 Withdrawal From Future Biomedical Research**

Participants may withdraw their consent for Future Biomedical Research. Participants may withdraw consent at any time by contacting the principal investigator for the main trial. If medical records for the main trial are still available, the investigator will contact the Sponsor using the designated mailbox ([contact]). Subsequently, the participant's consent for Future Biomedical Research will be withdrawn. A letter will be sent from the Sponsor to the investigator confirming the withdrawal. It is the responsibility of the investigator to inform the participant of completion of withdrawal. Any analyses in progress at the time of request for withdrawal or already performed prior to the request being received by the Sponsor will continue to be used as part of the overall research trial data and results. No new analyses would be generated after the request is received.

In the event that the medical records for the main trial are no longer available (eg, if the investigator is no longer required by regulatory authorities to retain the main trial records) or the specimens have been completely anonymized, there will no longer be a link between the participant's personal information and their specimens. In this situation, the request for specimen withdrawal cannot be processed.

#### **9.1.10 Participant Blinding/Unblinding**

This is an open label trial; there is no blinding for this trial.

#### **9.1.11 Calibration of Equipment**

The investigator or qualified designee has the responsibility to ensure that any device or instrument used for a clinical evaluation/test during a clinical trial that provides information about inclusion/exclusion criteria and/or safety or efficacy parameters shall be suitably calibrated and/or maintained to ensure that the data obtained is reliable and/or reproducible. Documentation of equipment calibration must be retained as source documentation at the trial site.

## **9.2 Efficacy Assessments**

### **9.2.1 Tumor Imaging and Assessment of Disease**

The process for image collection and transmission to the central imaging vendor can be found in the Site Imaging Manual (SIM). Tumor imaging should be acquired by computed tomography (CT, strongly preferred). Magnetic resonance imaging (MRI) should be used when CT is contraindicated or for imaging in the brain. The same imaging technique regarding modality and use of contrast should be used in a participant throughout the trial to optimize the visualization of existing and new tumor burden. Baseline imaging should include head, neck, chest, abdomen, and pelvis; imaging of the affected extremities is required for those participants with disease in the extremities at baseline. Please refer to the SIM for further guidance on required imaging at scheduled assessments.

Note: imaging of the pelvis is not required after the baseline image is obtained with the exception of the primary involvement of the pelvis and lower extremities.

Expedited confirmation of measurable disease based on RECIST 1.1 by the central imaging vendor at screening will be used to determine participant eligibility. Confirmation of measurable disease by the central imaging vendor per RECIST 1.1 is required prior to participant enrollment. Although RECIST 1.1 references a maximum of 5 target lesions in total and 2 per organ, MSD allows a maximum of 10 target lesions in total and 5 per organ. For participants with no RECIST 1.1 measurable disease visualized by CT or MRI, participants with cutaneous lesions will be considered to have RECIST 1.1 measurable disease when the lesion is superficial and  $\geq 10$  mm in diameter when assessed using calipers.

All scheduled images for all study participants from the sites will be submitted to the central imaging vendor. In addition, additional imaging (including other modalities) that are obtained at an unscheduled time point to determine disease progression, as well as imaging obtained for other reasons but captures radiologic progression, should be submitted to the central imaging vendor as well. Image submission requirements include imaging acquired at off-site facilities while participant is on trial.

#### **9.2.1.1 Initial Tumor Imaging**

Initial tumor imaging including any digital photography at screening must be performed within 28 days prior to the date of treatment allocation. The site study team must review screening images to confirm the participant has measurable disease per RECIST 1.1 prior to submitting to the central vendor. The screening images must be submitted to the central imaging vendor for confirmation of measurable disease per RECIST 1.1 for eligibility prior to randomization.

Scans performed as part of routine clinical management are acceptable for use as screening tumor imaging if they are of diagnostic quality, performed within 28 days prior to the date of randomization, and can be assessed by the central imaging vendor.

Participants with previously treated brain metastases may participate provided they have stable brain metastases, ie, without evidence of progression by imaging [confirmed by MRI if MRI was used at prior imaging, or confirmed by CT imaging if CT was used at prior imaging] for at least 4 weeks prior to the first dose of trial treatment. Any neurologic symptoms must have returned to baseline and participants must have no evidence of new or enlarging brain metastases, and have not used steroids for brain metastases for at least 7 days prior to trial initiation as per local site assessment. This exception does not include carcinomatous meningitis, as participants with carcinomatous meningitis are excluded regardless of clinical stability.

### **9.2.1.2 Tumor Imaging During the Trial**

The first on-study imaging assessment should be performed at 6 weeks (42 days + 7 days) from the date of treatment allocation. Subsequent tumor imaging should be performed every 6 weeks (42 days  $\pm$  7 days) or more frequently if clinically indicated through Year 1. After 1 year, participants who remain on treatment will have imaging performed every 9 weeks (63 days  $\pm$  7 days). Imaging timing should follow calendar days and should not be adjusted for delays in cycle starts. Imaging should continue to be performed until disease progression (unless site principal investigator [PI] elects to continue treatment and follow irRECIST), the start of new anti-cancer treatment, withdrawal of consent, death, or notification by the Sponsor, whichever occurs first. Following first radiographic indication of disease progression, participant management should shift to irRECIST and disease progression should be confirmed at least 4 weeks after the first scan indicating PD in clinically stable participants. All supplemental imaging must be submitted to the central imaging vendor.

Per RECIST 1.1\*, PR and CR should be confirmed by a repeat tumor imaging assessment obtained 4 weeks or longer from the date the response was first documented. The tumor imaging performed to confirm a response should be performed at the earliest 4 weeks after the first indication of response, or at the next scheduled scan. Participants who obtain a confirmation scan do not need to undergo the next scheduled tumor imaging if it is  $\leq$  4 weeks later; tumor imaging may resume at the subsequent scheduled imaging time point. \*For participants who were deemed eligible via digital photography and who have obtained a CR, a biopsy is required to be submitted for central pathology review to confirm CR within 30 days of initial confirmation. For participants who have obtained a CR prior to the release of Amendment 03, a biopsy is required within 30 days of protocol Amendment 03 approval in their respective countries for submission to central pathology review (see Section 9.2.1.8).

Per irRECIST (Section 9.2.1.6.), disease progression should be confirmed by the site at least 4 weeks after site-assessed first radiologic evidence of PD in clinically stable participants. Participants who have unconfirmed disease progression may continue on treatment at the discretion of the site investigator until progression is confirmed by the site, provided they have met the conditions detailed in Section 9.2.1.6. Participants who obtain a confirmation scan do not need to undergo the next scheduled tumor imaging if it is  $\leq$  4 weeks later; tumor imaging may resume at the subsequent scheduled imaging time point if clinically stable. Participants who have confirmed disease progression as assessed by the site will discontinue trial treatment. Exceptions are detailed in Section 9.2.1.6.

### **9.2.1.3 End of Treatment and Follow-up Tumor Imaging**

For participants who discontinue study treatment, tumor imaging should be performed at the time of treatment discontinuation ( $\pm 4$  week window). If previous imaging was obtained within 4 weeks prior to the date of discontinuation, then imaging at treatment discontinuation is not required and the participant should continue with the protocol specified tumor imaging time points. For participants who discontinue study treatment due to documented disease progression, this is the final required tumor imaging if the Investigator elects not to implement irRECIST.

In participants who discontinue trial treatment without documented disease progression, every effort should be made to continue monitoring their disease status by tumor imaging using the same imaging schedule used while on treatment (every 6 weeks in Year 1 or 9 weeks after Year 1) to monitor disease status until the start of new anti-cancer treatment, disease progression, death, or the end of the trial, whichever occurs first.

### **9.2.1.4 Second Course (Retreatment) Tumor Imaging**

Tumor imaging including any digital photography must be performed within 28 days prior to restarting treatment with pembrolizumab. Local reading (investigator assessment with site radiology reading) will be used to determine eligibility. Imaging should be submitted to the central imaging vendor for retrospective review.

Note: imaging of the pelvis is not required prior to restarting treatment with pembrolizumab with the exception of the primary involvement of the pelvis and lower extremities during the initial treatment phase.

The first on trial imaging assessment should be performed at 6 weeks (42 days + 7 days) after the restart of treatment. Subsequent tumor imaging should be performed every 6 weeks (42 days  $\pm$  7 days) or more frequently if clinically indicated.

If tumor imaging shows initial PD per RECIST 1.1, tumor assessment should be repeated  $\geq 4$  weeks later in order to confirm PD with the option of continuing treatment while awaiting radiologic confirmation of progression. Participants who obtain a confirmation scan do not need to undergo scheduled tumor imaging if it is 4 weeks later and may wait until the next scheduled imaging time point if clinically stable.

Imaging should continue to be performed until disease progression, the start of new anti-cancer treatment, withdrawal of consent, death, or notification by the Sponsor, whichever occurs first. Disease progression may be confirmed at least 4 weeks after the first tumor imaging indicating PD in clinically stable participants. Additional irRECIST details are described in Section 9.2.1.6.

In participants who discontinue trial treatment, tumor imaging should be performed at the time of treatment discontinuation ( $\pm$  4 week window). If a previous scan was obtained within 4 weeks prior to the date of discontinuation, then a scan at treatment discontinuation is not mandatory. In participants who discontinue trial treatment due to documented disease progression, this is the final required tumor imaging.

In participants who discontinue trial treatment without documented disease progression, every effort should be made to continue monitoring their disease status by radiologic imaging every 6 weeks (42 days  $\pm$  7 days) until either the start of a new anti-cancer treatment, disease progression, death, or the end of the trial, whichever occurs first.

### **9.2.1.5 RECIST 1.1 Assessment of Disease**

RECIST 1.1 will be used by BICR as the primary measure for assessment of tumor response, date of disease progression, and as a basis for all protocol guidelines related to disease status (eg, discontinuation of trial therapy). Although RECIST 1.1 references a maximum of 5 target lesions in total and 2 per organ, the Sponsor allows a maximum of 10 target lesions in total and 5 per organ, if clinically relevant to enable a broader sampling of tumor burden.

### **9.2.1.6 irRECIST Assessment of Disease**

Immune-related RECIST is RECIST 1.1 adapted as described below to account for the unique tumor response seen with immunotherapeutic drugs. Immune-related RECIST will be used by the site investigator/local radiology reviewers to confirm tumor response and progression, and make treatment decisions. This data will be collected in the clinical database.

When feasible, participants treated with pembrolizumab should not be discontinued until progression is confirmed by the local site investigator/radiology assessment. This allowance to continue treatment despite initial radiologic PD takes into account the observation that some participants can have a transient tumor flare in the first few months after the start of immunotherapy, and then experience subsequent disease response. Participants that are deemed clinically unstable are not required to have repeat tumor imaging for confirmation of PD. Tumor flare includes any of the following scenarios:

- Worsening of existing target lesion(s)
- Worsening of existing non-target lesion(s)
- Development of new lesion(s)

In participants treated with pembrolizumab who have shown initial evidence of radiological PD by RECIST 1.1 as assessed by the site, it is at the discretion of the PI whether to continue a participant on trial medication until repeat imaging is obtained (using irRECIST for participant management) (Table 8 and Figure 2). This clinical judgment decision by the site investigator should be based on the participant's overall clinical condition, including performance status, clinical symptoms, and laboratory data. Participants may receive trial

medication and the tumor assessment should be repeated  $\geq 4$  weeks later in order to confirm PD by irRECIST per site assessment. Clinical stability is defined as the following:

- Absence of symptoms and signs indicating clinically significant progression of disease, including worsening of laboratory values
- No decline in ECOG performance status
- Absence of rapid progression of disease
- Absence of progressive tumor at critical anatomical sites (eg, cord compression) requiring urgent alternative medical intervention

Any participant deemed **clinically unstable** should be discontinued from trial treatment at site-assessed first radiologic evidence of PD and is not required to have repeat imaging for PD confirmation.

In determining whether or not the tumor burden has increased or decreased per irRECIST, the local site investigator should consider all target and non-target lesions, as well as any incremental new lesion(s).

Disease progression will be considered to be “not confirmed” at repeat imaging if ALL of the following occur (as assessed by irRECIST):

- Target lesion sum of diameters is  $<20\%$  or  $<5$  mm absolute increase compared to nadir
- Non-target disease resulting in initial PD is stable or qualitatively improved
- New lesion resulting in initial PD is stable or qualitatively improved
- No incremental new lesion(s) since last evaluation
- No incremental new non-target lesion progression since last evaluation

If repeat imaging does not confirm PD per irRECIST as assessed by the local site investigator and the participant continues to be clinically stable, treatment may continue and follow the regular imaging schedule.

Disease progression will be considered to be “confirmed” at repeat imaging if ANY of the following occur (as assessed by irRECIST):

- Target lesion sum of diameters remains  $\geq 20\%$  and at least 5 mm absolute increase compared to nadir
- Non-target disease resulting in initial PD is qualitatively worse
- New lesion resulting in initial PD is qualitatively worse
- Additional new lesion(s) since last evaluation
- Additional new non-target lesion progression since last evaluation

If repeat imaging confirms PD due to any of the scenarios listed above, participants will be discontinued from trial therapy.

**NOTE:** If a participant has confirmed radiographic progression (ie, 2 scans at least 4 weeks apart demonstrating PD) per irRECIST, but the participant is achieving a clinically meaningful benefit, and there is no further increase in the tumor burden at the confirmatory tumor imaging, an exception to continue treatment may be considered following consultation with the Sponsor. In this case, if treatment is continued, tumor imaging should continue to be performed following the intervals as outlined in Section 2.0 and be submitted to the central imaging vendor.

Note: A new primary low-risk cSCC lesion is not considered as a PFS event. A new primary low-risk cSCC should be in an anatomically separate site to the original (Index) cSCC site. A new lesion(s) in close proximity ( $\leq 5$  cm from the index lesion) to the index cSCC lesion site should be considered a recurrence unless the lesion originates from the epidermis and is completely contained within the dermis with epidermal connection and contains no “high risk” features (outlined below). Discussion with the Medical Monitor is required where there is uncertainty of new primary cSCC lesion vs recurrence of a lesion. If the new lesion does not originate from the epidermis and is confined to the dermis without epidermal connection or invading subcutaneous fat tissue, the lesion will be considered as “in-transit metastasis” and will be deemed as an event.

For a lesion to be considered “low risk” per NCCN Guidelines [National Comprehensive Cancer Network 2017], the histopathology report needs to confirm the following; well or moderately differentiated lesion, no adenoid, adenosquamous, desmoplastic, or metaplastic subtypes, <2mm in thickness and no perineural, lymphatic, or vascular involvement.

Discussion with the Sponsor is required if these criteria are not met and the investigator assesses the new lesion as consistent with a new primary cSCC.

Additional details about irRECIST are provided in the MSD TIP Sheet for RECIST 1.1 and irRECIST.

Table 8 Imaging and Treatment After First Radiologic Evidence of Progressive Disease

	Clinically Stable		Clinically Unstable	
	Imaging	Treatment	Imaging	Treatment
First radiologic evidence of PD by RECIST 1.1	Repeat imaging at $\geq 4$ weeks at site to confirm PD	May continue trial treatment at the local site investigator's discretion while awaiting confirmatory tumor imaging by site by irRECIST	Repeat imaging at $\geq 4$ weeks to confirm PD per physician discretion only	Discontinue treatment
Repeat tumor imaging confirms PD by irRECIST at the local site	No additional imaging required	Discontinue treatment (exception is possible upon consultation with Sponsor)	No additional imaging required	Not applicable
Repeat tumor imaging shows SD, PR, or CR by irRECIST at the local site	Continue regularly scheduled imaging assessments	Continue trial treatment at the local site investigator's discretion	Continue regularly scheduled imaging assessments	May restart trial treatment if condition has improved and/or clinically stable per investigator's discretion. Next tumor image should occur according to the regular imaging schedule.

CR = complete response; irRECIST = immune-related response evaluation criteria in solid tumors; PD = progressive disease; PR = partial response; RECIST = response evaluation criteria in solid tumors; SD = stable disease

[figure not shown]

Figure 2 Imaging and Treatment for Clinically Stable Participants After First Radiologic Evidence of PD Assessed by the Site

### 9.2.1.7 Photography for Cutaneous Lesions

For participants without RECIST 1.1 measurable disease on CT or MRI scans, digital photographs documenting RECIST 1.1 measurable cutaneous lesions must be obtained if the cutaneous lesion is included as part of the target lesions assessment according to RECIST 1.1. Target cutaneous lesions are defined as superficial lesions which are  $\geq 10$  mm diameter as assessed using calipers. Any target skin lesion must be followed using color photography which includes a ruler to estimate lesion size. Specific guidance on how to acquire digital photographs of skin lesions will be provided in the SIM. Any malignant cutaneous lesion  $< 10$  mm in diameter can be followed as non-target disease. Copies of the color digital photograph must be forwarded to the central imaging vendor for assessment. The timing for capturing cutaneous lesion photographs must follow the same schedule as the imaging scans. The requirements de-identifying and transmitting the digital photographs to the central imaging vendor are located in the SIM.

### **9.2.1.8 Tumor Tissue Collection and Assessment of Disease Recurrence**

For participants without RECIST 1.1 measurable disease on CT or MRI scans that were deemed eligible by digital photography only (see Section 9.2.1.7), a tissue biopsy is required within 30 days of investigator-determined CR and submitted for central pathology review and confirmation of the absence of disease. For participants considered to have obtained CR prior to the release of Amendment 03, a biopsy is required within 30 days of Protocol Amendment 03 approval in their respective countries.

The study pathologists will send the representative specimens (slides) for central pathology review, as detailed in the Vendor Manual. The Vendor Manual will outline the standard guidelines for pathological evaluation of specimens. A summary note will be provided to the study pathologist that includes a general overview of the study.

Communication from surgeon to local pathologist should follow local practice and institutional guidelines. Detailed instructions for tissue collection, processing and shipment are provided in the Vendor Manual.

In the absence of biopsy confirmed CR, response assessment will be considered as PR; stable disease is not considered a response.

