**7.2.2 Second Course Phase (Retreatment) for Pembrolizumab (MK-3475)**

All participants who stop study treatment with SD or better may be eligible for up to an additional 17 cycles (approximately 1 year) of pembrolizumab treatment if they progress after stopping trial treatment from the initial treatment phase. This retreatment is termed the Second Course Phase of this trial and is only available if the trial remains open and the participant meets the following conditions:

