## **7.7 Concomitant Therapy**

Medications or vaccinations specifically prohibited in the exclusion criteria are not allowed during the ongoing trial. If there is a clinical indication for any medication or vaccination specifically prohibited during the trial, discontinuation from trial therapy or vaccination may be required. The investigator should discuss any questions regarding this with the Sponsor Clinical Director. The final decision on any supportive therapy or vaccination rests with the investigator and/or the participant's primary physician. However, the decision to continue the participant on study treatment requires the mutual agreement of the investigator, the Sponsor and the participant.

Listed below are concomitant medications/therapies that are prohibited during the course of the trial:

- Surgical intervention to a target lesion

Note: During study treatment surgical intervention to the disease under study is prohibited. This restriction applies to all skin lesions including actinic keratosis, target or non-target lesions. If a lesion is biopsied (not completely resected) and the histology is identified as different than cSCC, the case must be discussed between the investigator and Sponsor; if the biopsy result of a lesion biopsy confirms cSCC, this would be considered progressive disease leading to possible early discontinuation of study treatment.

- Antineoplastic systemic chemotherapy or biological therapy
- Immunotherapy not specified in this protocol (other than denosumab for bone metastasis)
- Chemotherapy not specified in this protocol
- Investigational agents other than pembrolizumab
- Radiation therapy

Note: Radiation therapy to a symptomatic solitary nontarget lesion or to the brain may be allowed at the investigator's discretion.

- Live or live attenuated vaccines within 30 days prior to the first dose of trial treatment and while participating in the trial. Examples of live vaccines include, but are not limited to, the following: measles, mumps, rubella, varicella/zoster, yellow fever, rabies, BCG, and typhoid vaccine. Seasonal influenza vaccines for injection are generally killed-virus vaccines and are allowed; however, intranasal influenza vaccines (eg, FluMist®) are live-attenuated vaccines and are not allowed.

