## **8. Discontinuation/Withdrawal Criteria**

### **8.1 Discontinuation of Study Treatment**

Discontinuation of study treatment does not represent withdrawal from the study.

As certain data on clinical events beyond study treatment discontinuation may be important to the study, they must be collected through the participant's last scheduled follow-up, even if the participant has discontinued study treatment. Therefore, all participants who discontinue study treatment prior to completion of the protocol-specified treatment period will still continue to participate in the study as specified in Section 2 – Schedule of Activities and Section 9.10.3 – Discontinued Participants Continuing to be Monitored in the Study.

Participants may discontinue study treatment at any time for any reason or be dropped from the study treatment at the discretion of the investigator should any untoward effect occur. In addition, a participant may be discontinued from study treatment by the investigator or the Sponsor if study treatment is inappropriate, the trial plan is violated, or for administrative and/or other safety reasons. Specific details regarding procedures to be performed at study treatment discontinuation are provided in Section 9.1.9 – Withdrawal/Discontinuation.

A participant must be discontinued from study treatment but continue to be monitored in the study for any of the following reasons:

- The participant or participant's legally acceptable representative requests to discontinue study treatment.
- The participant has a medical condition or personal circumstance which, in the opinion of the investigator and/or Sponsor, placed the participant at unnecessary risk from continued administration of study treatment.
- The participant has a confirmed positive serum pregnancy test.
- Confirmed radiographic disease progression outlined in Section 9.2.1.6 (after obtaining informed consent addendum and Sponsor communication, the investigator may elect to continue treatment beyond disease progression)
- Any progression or recurrence of any malignancy, or any occurrence of another malignancy that requires active treatment
- Any study intervention-related toxicity specified as a reason for permanent discontinuation as defined in the guidelines for dose modification due to AEs in Section 7.2

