### **9.10.3 Discontinued Participants Continuing to be Monitored in the Study**

Participants who discontinue study treatment for a reason other than disease progression will be considered as on study and should continue with regularly scheduled assessments including collecting participant information on the start of new anticancer therapy, disease progression, and death.

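### The 7.7 note on lesion biopsies does not exempt the biopsy that 9.2.1.8 requires at complete response, so read literally it calls residual cSCC progression where 9.2.1.8 makes it a PR (minor)

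*Combined protocol and SAP*

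**What the plan says.** Section 9.2.1.8 applies to participants with no measurable disease on CT or MRI who were eligible by digital photography only. It requires a biopsy, read by central pathology, within 30 days of the investigator's call of CR. It gives one consequence if the biopsy does not confirm the CR: "In the absence of biopsy confirmed CR, response assessment will be considered as PR; stable disease is not considered a response".

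Section 7.7 carries a note under the prohibition of surgery to a target lesion. The note applies during study treatment and to all skin lesions, target and non-target. For a lesion that is biopsied but not completely resected, it gives two outcomes. Histology other than cSCC goes to discussion with the Sponsor. Otherwise, "if the biopsy result of a lesion biopsy confirms cSCC, this would be considered progressive disease leading to possible early discontinuation of study treatment".

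Section 9.2.1.5 says "RECIST 1.1 will be used by BICR as the primary measure for assessment of tumor response, date of disease progression", and goes on to make RECIST 1.1 the basis for protocol guidance on disease status, with discontinuation as its example. The Synopsis likewise has treatment continue until the site assesses progression per RECIST 1.1. A footnote to that statement leads to the CR biopsy, whose purpose it gives as confirming the CR.

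**The concern.** The same pathology result gets two labels. Under 9.2.1.8, cSCC found where a target lesion has cleared means incomplete clearance, hence PR. Under 7.7, read literally, it is progression. Neither section refers to the other. The other statements of the biopsy rule (Synopsis, both Schedules of Activities, 5.1 and 9.2.1.2) carry no exemption either.

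The 7.7 label makes no clinical sense here: a target lesion in this trial is already cSCC, so finding cSCC in it is not evidence of growth. At stake is the care of a responding participant, who could be labelled as progressed and taken off treatment because of a test the protocol itself requires.

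**Working it through.** The plan attaches no figure to this point, so the main check sets the texts side by side.

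**1. Does the 7.7 note reach this biopsy?**
- Lesion: the note names target lesions. In photography-only participants these are cutaneous (9.2.1.7).
- Timing: the note applies during study treatment. Section 8.1 allows stopping for CR only after at least 8 cycles and at least 2 doses beyond the CR, so a biopsy due within 30 days of CR will usually fall on treatment.
- Type: the note covers biopsy without complete resection, which a CR biopsy can be.

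On its wording, it reaches this biopsy.

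**2. Which rule should govern?** Section 9.2.1.8 has the narrower scope, a stated time and a stated outcome. Section 9.2.1.5 and the Synopsis tie discontinuation to RECIST 1.1. All of this points to PR, but no sentence says so.

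**3. What follows if a site applies 7.7?**
- Section 8.1 lists among reasons for stopping: "Any progression or recurrence of any malignancy, or any occurrence of another malignancy that requires active treatment". The closing condition may limit the item to disease needing active treatment.
- The option to treat until progression is confirmed is written for radiologic progression: "In participants treated with pembrolizumab who have shown initial evidence of radiological PD by RECIST 1.1 as assessed by the site". Progression called on histology has no stated confirmation step.
- Second-course eligibility begins: "All participants who stop study treatment with SD or better may be eligible for up to an additional 17 cycles". A stop recorded as progression fails this.
- Continued assessment is described thus: "Participants who discontinue study treatment for a reason other than disease progression will be considered as on study and should continue with regularly scheduled assessments". A stop recorded as progression falls outside it.

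**4. Upper bound on treatment forgone.** Assume dosing on days 0, 21, 42 and so on without delay, nominal image dates, and a stop at the 30-day biopsy deadline. Infusions given = floor((CR day + 30)/21) + 1.

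| CR first called | Deadline | Given | Forgone of 35 |
|---|---|---|---|
| Week 6 (day 42) | day 72 | 3 + 1 = 4 | 31 |
| Week 24 (day 168) | day 198 | 9 + 1 = 10 | 25 |
| Week 48 (day 336) | day 366 | 17 + 1 = 18 | 17 |

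Up to 17 second-course infusions could be lost as well. These are worst cases. They assume that pathology takes no time and that the participant would otherwise have completed all 35. The further 17 also assume later progression and eligibility for retreatment.

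**5. Endpoints.** Section 10.4.1 counts CR or PR in ORR, DCR and DOR, so changing CR to PR alters none of these. Section 10.6.1.2 dates PFS progression by BICR per RECIST 1.1. A site label under 7.7 is therefore not itself a PFS or DOR event. It could end imaging or lead to new therapy. If new therapy starts without progression or death, Table 11 censors DOR at the last adequate assessment before it.

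**6. Can a response be lost from ORR?** Take the CR image as day 0.
- If an image at least 4 weeks earlier showed PR, the CR image already confirms the response. Loss therefore needs the CR image to be the first response.
- Section 9.2.1.3 says: "If previous imaging was obtained within 4 weeks prior to the date of discontinuation, then imaging at treatment discontinuation is not required". A stop by day 28 thus needs no further image. From day 29 one is required, within 4 weeks either side (for day 29, days 1 to 57).
- An image on day 28 or later meets the 4-week confirmation rule.

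So loss also needs either biopsy, result and stop all within 28 days, or a discontinuation image taken before day 28, and no later confirming image. The waiver window is 30 − 28 = 2 days shorter than the biopsy deadline, before any pathology turnaround.

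**7. Scale of one such loss.** The Clopper-Pearson limits are the 0.025 quantile of Beta(r, n − r + 1) and the 0.975 quantile of Beta(r + 1, n − r). For 20/50 they give 26.4% to 54.8%, matching Table 14; for 30/100 they give 21.2% to 40.0%, matching Table 13. One responder fewer gives:
- LA: 19/50 = 38.0% (24.7% to 52.8%), a change of 1/50 = 2.0 points.
- R/M: 29/100 = 29.0% (20.4% to 38.9%), a change of 1/100 = 1.0 point.

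**The case against.** The strongest reply is that the 7.7 note was never meant for this biopsy. It sits under a ban on surgery to target lesions and suits new or suspicious lesions biopsied outside the protocol plan. Applied to the CR biopsy, it misfires on both branches. A clear biopsy could send every confirmed CR to Sponsor discussion, and a positive one would be progression merely for having the histology required at entry. Section 9.2.1.8 is the specific rule, and RECIST 1.1 is the stated basis for stopping. Even under 7.7, discontinuation is only possible. The radiographic-progression item in 8.1 also lets the investigator continue after additional consent and communication with the Sponsor.

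Most of this stands. It settles which reading is better, shows that no stop is mandated, and makes the point minor. It does not remove the conflict. The note names target lesions, exempts nothing, and is where an investigator would look for the meaning of a biopsy result during treatment. That the specific rule prevails is an inference each site must make.

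**Conclusion.** The inconsistency is in the current text, and its severity is minor. The better reading is that residual cSCC in the required biopsy is a PR and treatment goes on. The risk is that a site follows 7.7 literally, labels a responder as progressed, stops treatment and removes second-course eligibility.

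A reader might infer that the plan miscounts responders or creates false PFS or DOR events. The documents do not support that: BICR per RECIST 1.1 sets response and the progression date, and CR and PR count alike. Loss from ORR is conceivable only along the narrow path in step 6. A reader might also infer that stopping is compulsory; 7.7 does not say so.

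Frequency is unknown. The documents give neither the number of photography-only participants nor the share of CR biopsies that are positive. The Vendor Manual, to which 9.2.1.8 refers pathology handling, was not available and might already address the point.

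**What to change.** Add to the 7.7 note that it does not apply to the biopsy required by 9.2.1.8. Residual cSCC in that biopsy changes CR to PR and is not progressive disease unless RECIST 1.1 criteria for progression are also met; treatment and scheduled assessments continue.

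The cost is a short insertion, with no extra biopsy, image or visit. Any positive CR biopsy already handled as progression should have its case reviewed.

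Two clarifications are optional and not part of the defect. Section 10.4.1 could state that central pathology changes CR to PR only and sets no progression or censoring date. The 30-day clock could also be counted everywhere from the investigator's call of CR. The Synopsis, 5.1 and 9.2.1.8 count it from the CR, whereas 9.2.1.2 and both Schedules of Activities count it from initial confirmation. A biopsy within 30 days of the first CR already satisfies all six.
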